4. STUDY ENROLLMENT AND WITHDRAWAL

4.1 PARTICIPANT INCLUSION CRITERIA

To be eligible to participate in this study, an individual must meet all of the following criteria:

1. Ability to understand and the willingness to sign a written informed consent document.
2. Age ≥ 18 years at time of informed consent. Both men and women and members of all races and ethnic groups will be included.
3. Morphologically documented relapsed/refractory AML as defined by World Health organization (WHO) criteria after at least 1 prior therapy for AML with the exception of hydroxyurea, and not felt to have curative treatment options per treating physician, or the patients themselves are unwilling to consider curative treatment options.
4. Sufficient and viable bone marrow aspirate or peripheral blood collection to use for the *ex vivo* sensitivity assay.
5. ECOG performance status 0 to 2 (Refer to Appendix A)
6. Women must not be pregnant or breastfeeding. Women of childbearing potential must have a negative serum or urine pregnancy test within 14 days prior to start of study drug administration.
7. Participants must agree to use an adequate method contraception (see Appendix C).
8. Must be able to take oral medications.
9. Adequate organ function as defined by the following:
 - a. Serum creatinine $\leq 2 \times$ the upper limit of normal (ULN), or glomerular filtration rate $> 20 \text{ ml/min}$ as calculated by Cockcroft-Gault formula.
 - b. Serum potassium, magnesium, and calcium (corrected for albumin) within institutional normal limits or can be corrected with supplementation.
 - c. Total serum bilirubin $\leq 2.5 \times$ ULN.
 - d. Serum aspartate transaminase (AST) and/or alanine transaminase (ALT) $\leq 2.5 \times$ ULN.

4.2 PARTICIPANT EXCLUSION CRITERIA

An individual who meets any of the following criteria will be excluded from participation in this study:

1. Diagnosis of acute promyelocytic leukemia (APL, or AML M3 subtype)
2. Active central nervous system involvement with AML
3. Concurrent active malignancy with expected survival of less than 1 year. For example, candidates with treated skin cancers, prostate cancer, breast cancer, etc. without metastatic disease are candidates for therapy since their expected survival exceeds that of relapsed or refractory AML. All subjects with concurrent malignancies will be reviewed by the PI prior to enrollment.
4. Clinically significant GVHD or active GVHD requiring initiation or escalation of treatment within 28 day screening period.

5. Clinically significant coagulation abnormality, such as disseminated intravascular coagulation.
6. Participants who are currently receiving any other investigational agents.
7. Previous treatment with CSF-1R kinase inhibitor or CSF-1R blocking antibody.
8. Known clinically significant liver disease defined as ongoing drug-induced liver injury, chronic active hepatitis C (HCV), chronic active hepatitis B (HBV), alcoholic liver disease, non-alcoholic steatohepatitis, primary biliary cirrhosis, extrahepatic obstruction caused by cholelithiasis, cirrhosis of the liver, portal hypertension, or history of autoimmune hepatitis.
9. Untreated HIV or active hepatitis C detectable by PCR, or chronic hepatitis B (patients positive for hepatitis B core antibody who are receiving IVIG are eligible if HepB PCR is negative).
10. Known history of cerebrovascular accident, myocardial infarction, or intracranial hemorrhage within 2 months of enrollment.
11. Clinically significant surgery within 2 weeks of enrollment.
12. Per PI discretion, active infection that is not well controlled by antibacterial or antiviral therapy.
13. Cancer-directed therapy within 2 weeks prior to starting treatment, with the exception of hydroxyurea, which is allowed to control white blood cell count. Hydroxyurea will be weaned as soon as clinically feasible.
14. Unwillingness to receive infusion of blood products.
15. Drugs that affect the CYP3A4 systems are allowed and essential for cancer patients, including anti-fungals but should be used with caution.
16. Patients with uncontrolled white blood cell count (defined as >50 K/cu mm not controlled with hydrea).

4.3 STRATEGIES FOR RECRUITMENT AND RETENTION

Participants for this study will be recruited from within the hematology and oncology practices participating research sites. Participants may be identified and referred to this study by their primary treating physician from the outside community. Participants may also initiate contact with the investigator through information of this study posted on the clinicaltrials.gov website.

4.3.1 ACCRUAL ESTIMATES

The number of participants to be accrued is driven by the study primary objective. An estimated 28 participants across OHSU and 2 participating sites will be recruited over a 24 month period.

No OHSU Knight Cancer Institute study will focus on any particular gender, racial or ethnic subset. No participant will be excluded from the study on the basis of gender, racial or ethnic origin. Male, female and minority volunteers will be recruited for this study from the general population and approximately 50% men and 50% women will be studied. Gender-nonconforming and gender-fluid individuals as members of the general population will also be recruited.

The projected gender, racial, and ethnic composition of the study will represent that of the state of Oregon (**Table 3**).

Table 3. Projected accrual for present study based on Oregon population demographics

Ethnic Category	Sex/Gender					
	Females		Males		Total	
	n	%	n	%	n	%
Hispanic or Latino	2	6.4	2	6.3	4	12.7
Not Hispanic or Latino	11	38.7	11	37.9	21	76.6
Ethnic Category: Total of all participants*	13		13			100*
<hr/>						
Racial Category						
American Indian or Alaskan Native	1	3.9	1	3.9	2	7.8
Asian	1	2.2	1	2.2	1	4.4
Black or African American	0	1.1	0	1.0	1	2.1
Native Hawaiian or other Pacific Islander	0	0.2	0	0.2	0	0.4
White	12	44.2	12	43.4	25	87.6
Two or more races	1	1.9	1	1.8	1	3.7
Racial Category: Total of all participants*	15	50.5	15	49.5		100

Source: Adapted from U.S. Census Bureau, 2010.

*Totals may not equal 100 due to rounding.

4.3.2 INCLUSION OF CHILDREN

This protocol does not include children because no dosing or adverse event data are currently available on the use of this study agent in this way in persons <18 years of age; therefore, children are excluded from this study.

4.4 REGISTRATION PROCEDURES

4.4.1 PARTICIPANT REGISTRATION

4.4.1.1 OHSU Registration

This is a Phase II trial and there is no randomization.

Participants will be required to give written informed consent to participate in the study before any screening tests or evaluations are conducted that are not part of standard care.

Registration from all consented participants must be entered into the OHSU electronic Clinical Research Management System (CRMS, e.g., eCRIS). At a minimum, registration of OHSU participants will include:

- A completed Participant Registration Form
- A completed Eligibility Checklist signed by the Investigator
- Signed copies of the most recently IRB-approved, informed consent form and HIPAA

authorization

4.4.2 MULTICENTER REGISTRATION

The OHSU coordinating center study team will manage the participant registration process. Investigators, or study team designee, at participating sites will identify eligible participants and send source documents that support eligibility to OHSU for review and verification before the participating site may enroll and treat the participant.

The OHSU coordinating center team is responsible for verifying completeness of documents, entering registration information into the Knight CRMS, and assigning a study number/identifier for each individual participant. The OHSU coordinating center will send an email to the participating site to indicate whether or not a participant is eligible and will assign a participant number/identifier.

Registration at participating research site will include a minimum of the following:

- A completed Participant Enrollment Form
- A completed Eligibility Checklist signed by the Investigator
- De-identified source documentation of eligibility
- Signed copies of the most recently local IRB-approved, informed consent form and HIPAA authorization.

Each participating research site is expected to maintain a screening log of all participants who are approached for the study. The log documents an explanation for exclusion due to screen failure. This log should be submitted to the OHSU coordinating center on a regular basis. Participating sites are required to retain, in a confidential manner, sufficient information on each participant so that the participant may be contacted should the need arise

4.5 PARTICIPANT SCREENING AND ENROLLMENT

In order to participate in this study, signed informed consent must be obtained from the participant or the participant's legally acceptable representative. The current Institutional Review Board (IRB) approved informed consent must be signed and dated by each participant prior to undergoing any study procedures or before any prohibited medications are withheld from the participant in order to participate in this study.

This study consists of a 28 day screening period. Screening will begin once the participant has provided written informed consent to participate in the study and ends on Day 0 of the study. All screening and baseline evaluations will be performed during the screening phase. Eligible participant assignment to one of two treatment arms, *assay positive* or *assay negative*, based on results from *ex vivo* screening assay will occur no later than 14 days prior to starting treatment with study agent. Samples will be collected from study eligible participants no later than 14 days prior to initiating treatment with study agent. Day 1 of the clinical trial will be when participants are started on JNJ-40346527. Total accrual of all participants is anticipated to take a total of 24 months.

4.6 PARTICIPANT WITHDRAWAL OR DISCONTINUATION

Participants are free to withdraw consent and discontinue participation in the study at any time and without prejudice to further treatment. If a participant no longer wants to receive investigational product, but is willing to come for follow-up appointments, the participant's

request should be honored, if possible. The following are examples demonstrating why a participant's treatment might be discontinued.

- Toxicity precludes further study treatment.
- There is a need for any treatment not allowed by the protocol.
- The participant fails to meet the criteria for study treatment.
- Disease recurrence or progression.
- Investigator's discretion.

No further participant contact should be made if the participant withdraws consent for participation in the study. Information about the reason(s) for discontinuation and collection of any new or ongoing adverse events (AEs) should be collected at the time the participant withdraws consent.

For all other reasons for discontinuation from the study treatment phase, the participant should return to the clinic for the end of treatment (EOT) visit according to Section 7.

4.6.1 HANDLING PARTICIPANT WITHDRAWAL AND DISCONTINUATION

Participants that discontinue the first cycle without experiencing a DLT may be replaced. Participants may be replaced if they voluntarily withdraw from the protocol, or if the participant is taken off study per the PI's discretion for reasons such as continued noncompliance. Per 45 CFR 46, the reasons for withdrawal, if known, will be recorded.

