Exploratory Objectives	
1. Evaluate the pharmacokinetics of JNJ-40346527 and effective inhibition of CSF-1R in marrow aspirates using plasma inhibitory assays with established CSF-1R-sensitive cell lines.2. Identify the effect of JNJ-40346527 on leukemia cells and the immune microenvironment.3. Analyze the frequency of mutations using genomic DNA from leukemia participants to determine if there is a genetic signature that predicts response to JNJ-40346527.4. Using RNA sequencing (RNAseq), identify an expression signature in CSF-1R⁺ cells that predicts patient response.5. Evaluate the effect of JNJ-40346527 on immune cell populations (cytotoxic T cells, etc.) and phospho-signaling proteins by CyTOF analysis in pre- and post-treatment samples in order to identify biomarkers that predict patient response and prioritize potential combination strategies for future clinical trials.6. Determine how leukemia cells change in response to CSF-1R inhibition by assessing cells collected pre- and post-treatment using an ex vivo sensitivity to a panel of small molecule inhibitors to determine what new drug sensitivities may emerge in AML cells after CSF-1R inhibition.
Number of Participants	Up to 28 participants (14 in each arm) will be enrolled. There will be 7 patients in Stage I and 7 patients in Stage II with the total of 14 patients per arm. Given the expected accrual rate of 14 participants per year, the study is expected to take 36 months (24 months of accrual period and the minimum follow-up of 12 months).
Duration of Therapy	Participants demonstrating favorable response to treatment are eligible to continue additional cycles of study agent until disease progression, death, or investigator discretion.
Duration of Follow Up	Until death or minimum of 12 months follow-up from the last dose of JNJ-40346527.
Inclusion Criteria	
1. Ability to understand and the willingness to sign a written informed consent document.2. Age ≥ 18 years at time of informed consent. Both men and women and members of all races and ethnic groups will be included.3. Morphologically documented relapsed/refractory AML as defined by World Health organization (WHO) criteria after at least 1 prior therapy for AML with the exception of hydroxyurea, and not felt to have curative treatment options per treating physician, or the patients themselves are unwilling to consider curative treatment options.

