	
alcoholic steatohepatitis, primary biliary cirrhosis, extrahepatic obstruction caused by cholelithiasis, cirrhosis of the liver, portal hypertension, or history of autoimmune hepatitis.
 
Untreated HIV or active hepatitis C detectable by PCR, or chronic hepatitis B (patients positive for hepatitis B core antibody who are receiving IVIG are eligible if HepB PCR is negative).
 
9. Untreated HIV or active hepatitis C detectable by PCR, or chronic hepatitis B (patients positive for hepatitis B core antibody who are receiving IVIG are eligible if HepB PCR is negative).
 
10. Known history of cerebrovascular accident, myocardial infarction, or intracranial hemorrhage within 2 months of enrollment.
 
11. Clinically significant surgery within 2 weeks of enrollment.
 
12. Per PI discretion, active infection that is not well controlled by antibacterial or antiviral therapy.
 
13. Cancer-directed therapy within 2 weeks prior to starting treatment, with the exception of hydroxyurea, which is allowed to control white blood cell count. Hydroxyurea will be weaned as soon as clinically feasible.
 
14. Unwillingness to receive infusion of blood products.
 
15. Drugs that affect the CYP3A4 systems are allowed and essential for cancer patients, including anti-fungals but should be used with caution.
 
16. Patients with uncontrolled white blood cell count (defined as >50 K/cu mm not controlled with hydrea).

<hr/>	
Investigational Product(s)	JNJ-40346527 will be administered at a dose of 150 mg PO twice daily in continuous 28-day cycles
<hr/>	
Statistical Considerations	A Simon 2-stage minimax design will be used to determine clinical efficacy. For each arm, 7 participants will be enrolled in the first stage. If there is at least 1 response among the first 7 participants, the trial will proceed to the second stage and enroll an additional 7 participants. The treatment is considered promising if there are at least 3 responses among 14 participants. The study has 80% power to test the best objective response rate of 5% (poor) vs. 30% (desirable) using one-sided 5% significance level.
Efficacy Assessments	Assess the best objective response rate, duration of response to JNJ-40346527, overall survival and event-free survival in participants with relapsed/refractory AML as stratified by ex vivo

	sensitivity.

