10.1 ANALYSIS POPULATIONS

Most common analysis populations are described below:

Analysis Population	Definition	Endpoint
Intent to Treat (ITT)	Those who consent and are registered for the trial regardless of actual receipt of screening or treatment	Used to report accrual
Evaluable for Safety	Those who received at least one dose of JNJ 40346527	Incidence of DLT and SAE
Evaluable for Response	Those who received at least one cycle of JNJ 40346527 and have response measurements	Best objective response
Evaluable for Overall Survival and Event-Free Survival	Those who received at least one dose of JNJ 40346527 and have survival information	Overall survival

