10.2 DESCRIPTION OF STATISTICAL METHODS

10.2.1 ANALYSIS OF PRIMARY ENDPOINT(S)

A Simon 2-stage minimax design will be used to determine best objective response. For each arm, we will enroll 7 patients in the first stage. If there is at least 1 response among the first 7 patients, we will proceed to the second stage and enroll an additional 7 patients. The treatment is considered promising if we have at least 3 responses among 14 patients. We will estimate the best objective response and exact confidence interval using the binomial distribution for each arm separately.

Response assessment will be based on best objective response rates within the first 2 cycles of study drug, including CR, CR with inadequate bone marrow recovery, partial response, stable disease, or progressive disease as defined by Cheson et al.²⁰

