10.3 SAMPLE SIZE, POWER, ACCRUAL RATE AND STUDY DURATION

10.3.1 SAMPLE SIZE AND POWER

The sample size for each group was derived according to the 2-stage design with minimax criteria using the following parameter settings: 1) 80% power; 2) 5% significance level; 3) historical response rate of 5% (poor response), and 4) desired response rate of 30% (promising response).²¹ The sample size and power analyses were conducted using PASS 14 software (<http://www.ncss.com/software/pass/>). Based on the expected accrual rate of 14 participants per year, we anticipate this trial to take 36 months (24 months of accrual and 12 month of minimum follow-up).

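### Section 4.6.1 lets participants be replaced after their response is known, and no section says how a replaced participant counts in the 7 or 14, so type I error is not controlled

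*Combined protocol and SAP*

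**What the plan says.** Section 4.6.1 contains two replacement rules. The first is tied to cycle 1: "Participants that discontinue the first cycle without experiencing a DLT may be replaced". The second is not tied to any time: "Participants may be replaced if they voluntarily withdraw from the protocol, or if the participant is taken off study" at the PI's discretion, with continued noncompliance given as an example and not as a limit. Section 4.6 allows withdrawal at any time.

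The design is a two-stage rule applied to each arm separately. Section 10.2.1 says "If there is at least 1 response among the first 7 patients, we will proceed to the second stage", and then "The treatment is considered promising if we have at least 3 responses among 14 patients". The Synopsis gives the enrolment limit: "Up to 28 participants (14 in each arm) will be enrolled".

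Section 10.1 defines the population for best objective response as "Those who received at least one cycle of JNJ 40346527 and have response measurements". It makes no exception for someone who later withdraws or is replaced. Section 8.2 has response determined at the end of each cycle, and Section 7.2.5 schedules marrows on Day 29 of cycles 1, 2 and 3.

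**The concern.** The two-stage calculation assumes that the 7 and the 14 are fixed sets of patients, chosen without regard to outcome. The second rule in 4.6.1 does not protect that assumption. A participant can finish cycle 1, have a marrow showing no response, then withdraw or be taken off study, and be replaced. The trial is not randomised, everyone receives the same drug, and nothing requires the replacement decision to be made without knowledge of the response.

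No section says what then happens to the count. If the replaced participant leaves the 7 or 14, a known non-response is discarded, against 10.1. If both participants count, the arm has more than 14 evaluable patients and no cutoff is defined for that number. Neither case is the design that was sized in 10.3.1. At stake are the primary response rate, the stage 1 decision and the final decision in each arm.

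**Working it through.** **Inputs.** Section 10.3.1 gives "1) 80% power; 2) 5% significance level; 3) historical response rate of 5% (poor response), and 4) desired response rate of 30% (promising response"). The Synopsis adds "using one-sided 5% significance level". The decision rule in 10.2.1 is 7 then 7 more patients, continue with at least 1 response, promising with at least 3. The documents give no withdrawal or replacement rate, so that is varied below as an assumption.

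**The plan's own figure.** With Bin(n, p) the number of responses, the chance of declaring an arm promising is

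P(p) = sum over x = 1 to 7 of P[Bin(7, p) = x] × P[Bin(7, p) ≥ 3 − x].

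At p = 0.05:
- x = 1: 0.2573 × 0.0444 = 0.0114
- x = 2: 0.0406 × 0.3017 = 0.0123
- x ≥ 3: 0.0038
- Total: 0.0274 (0.0275 from the rounded terms)

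At p = 0.30 the same sum is 0.8101. A full search also returns 7/14 with cutoffs 1 and 3 as the minimax design. The stated design is therefore reproduced. The attained type I error is 2.7%, and 5% is a ceiling that the discrete rule does not use up.

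**A fixed number of selective replacements.** Suppose k1 known non-responders are replaced in stage 1 and k2 in stage 2. Each replacement gives the arm one more chance of a response, so the formula applies with 7 + k1 and 7 + k2 patients and unchanged cutoffs. The result is the same whether the replaced non-responder is dropped or kept, because the number of responses and the cutoff of 3 are the same. Only the denominator of the estimate differs: with four replacements, 3/14 = 21.4% or 3/18 = 16.7%.

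| Selective replacements in one arm | Type I error at p = 0.05 (range over how they split between stages) |
|---|---|
| 0 | 0.0274 |
| 1 | 0.032-0.034 |
| 2 | 0.037-0.041 |
| 3 | 0.042-0.048 |
| 4 | 0.047-0.056 |
| 5 | 0.053-0.065 |

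With four replacements, only the split with all four in stage 2 stays below 5% (0.0475). With five, every split exceeds 5%.

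**A replacement probability.** If each non-responder is replaced with probability w and then dropped, the response probability per slot becomes p / [p + (1 − p)(1 − w)]. At p = 0.05:
- w = 10%: per-slot rate 0.0552, type I error 0.036
- w = 20%: per-slot rate 0.0617, type I error 0.047
- w = 25%: per-slot rate 0.0656, type I error 0.055

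The 5% ceiling is reached at w of about 22%. The expected number of replacements for 14 slots is then 14 / (1 − 0.95 × 0.2215) − 14 = 3.7.

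**The stage 1 gate.** At a true 5% rate, the chance of at least 1 response is 1 − 0.95^7 = 30%. With two selective replacements in stage 1 it is 1 − 0.95^9 = 37%.

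**Replacement unrelated to response.** The per-slot rate stays at 5% and the type I error at 0.0274.

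**The case against.** Four points on the other side deserve weight.

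First, 4.6.1 does not name non-response or progression as a ground for replacement. The example given is noncompliance, and 4.6 lists progression as a reason to stop treatment. A reader might infer that the clause exists mainly to replace non-responders. The text does not say that. What stands is that the example is open-ended, and that voluntary withdrawal carries no condition at all.

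Second, a reader might infer that the plan permits a known non-response to be deleted. It does not: 10.1 keeps anyone with one cycle and response measurements in the analysis. The documents are silent on how a replaced participant counts. That silence is the defect, since keeping both participants leaves an arm larger than 14 with no cutoff for it.

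Third, the attained error of 2.7% leaves slack below 5%. Up to three selective replacements in an arm stay at or below 4.8%.

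Fourth, the cap of 14 per arm could be read as ruling out extra patients. If so, it contradicts the permission to replace, and the two have to be reconciled.

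**Conclusion.** The gap is real and worth closing. As written, 4.6.1 allows replacement after response is known, and no section fixes how such a participant counts, so type I error is not controlled. It rises from 2.7% with any outcome-driven replacement, can exceed 5% from four in one arm, and exceeds 5% under every split from five. If the replaced non-responder is dropped, the response estimate is also biased upward.

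A reader might conclude that the stated 5% error rate simply no longer holds. The documents do not support that. The excess over 5% needs about four or more selective replacements in an arm, or about 22% of non-responders replaced. Those rates are assumptions. Replacement unrelated to outcome does no harm to the error rate.

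**What to change.** Amend 4.6.1 so that no participant with a post-baseline response assessment is replaced, whatever the reason for leaving. That participant keeps the slot in the 7 or 14 and counts as a non-responder unless PR or better was documented. Leave the cycle 1 replacement rule as it is for participants without a response assessment. State how permitted replacements fit with the limits of 14 per arm and 28 in total, and report each replacement with its date and reason. Section 4.6.1 already records reasons for withdrawal where known.

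The cost is a short amendment. Some slots will be held by participants who withdraw after their first assessment, so the observed response rate may be slightly less favourable.

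The change should not be widened to allow replacement only of participants who never took study drug. That would abolish the cycle 1 rule. If all losses then counted as non-responses, power would be 0.778, 0.741 or 0.656 for an assumed 5%, 10% or 20% loss unrelated to outcome (response rate 0.30 × 0.95, 0.90 or 0.80 in the formula above).
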